6.3 Preparation and dispensation

Each study site will be supplied with study drug in packaging as described under investigational drug section. A unique medication number is printed on the study medication label. Investigator staff will identify the study medication kits to dispense to the participant by contacting the IRT and obtaining the medication number(s).

6.3.1 Handling of study treatment and other treatment

6.3.1.1 Handling of study treatment

Study drug must be received by a designated person at the study site, handled and stored safely and properly, and kept in a secured location to which only the Investigator and designated site personnel have access. Upon receipt, all study drug must be stored according to the instructions specified on the labels and in the Investigator's Brochure. Clinical supplies are to be dispensed only in accordance with the protocol. Technical complaints are to be reported to the respective Novartis CO Quality Assurance.

The Investigator must maintain an accurate record of the shipment and dispensing of study drug in a drug accountability log. Monitoring of drug accountability will be performed by field monitors during site visits or remotely and at the completion of the trial. Participants will be asked to return all unused study drug and packaging at the end of the study or at the time of discontinuation of treatment.

At the conclusion of the study, and as appropriate during the course of the study, the Investigator will return all unused study drug, packaging, drug labels, and a copy of the completed drug accountability log according to the instructions provided by Novartis or its agents.

6.3.2 Instruction for prescribing and taking study treatment

All eligible RRMS participants will receive treatment with open label ofatumumab; no randomization will be performed in this study. In general, administration instructions contained within the USPI for Kesimpta[®] should be followed. Administration of ofatumumab (at study site or at home) should occur after the study visit assessments are performed, if on the same day of the study visit.

Drug will be dispensed at scheduled visits throughout the treatment period. Ofatumumab injection will be administered via an initial dose regimen of 20mg at Baseline/Week 0 (Day 1), followed by Week 1 (Day 7), Week 2 (Day 14) and every month thereafter, beginning at Week 4 (Month 1) until Month 18. Additional efficacy and safety assessments will be evaluated during an optional 12-month open-label extension, necessitating ofatumumab monotherapy over the course of up to 30 months (see [Figure 3-1](#)).

At the Baseline/Week 0 visit, participants will receive the subcutaneous injection at the study site. Site personnel will provide training to the participants on the correct procedure for self-administration of the subcutaneous injections. The participant or a caregiver may inject the study medication under supervision of a healthcare professional. Documentation of injection procedure understanding by the participant and/or the caregiver must be documented in the source document. Participants should remain at study site under observation for approximately 1 hour following dosing at the Baseline/Week 0 visit, where post-dose vital signs will be collected. A longer observation period may be required if these vital signs are not within reasonable limits of the participant's baseline values.

Site staff should remove the study treatment from the refrigerator and allow the AI pen to reach room temperature in the unopened box (approximately 15-30 minutes) before self-injection by the participant. Used AI pens should be disposed of immediately after use in a sharps container.

A different body site (front of thighs, lower abdomen) should be chosen each time a dose is administered to reduce the risk of an injection-site reaction; investigator/qualified site staff/caregiver can also inject the study treatment in the outer upper arms. Each new injection should be given at least one inch from the previously used site. If administration is in the abdomen, the 2-inch area around navel should be avoided. Study treatment should also not be injected into areas where the skin is tender, bruised, red, or hard, or where the participant has scars or stretch marks.

Following the Baseline/Week 0 visit, sufficient study drug will be supplied to the participant to cover all home administrations. Participants may inject the study medication at home, if they demonstrated ability to self-administer injections. If a participant is unable/unwilling to self-administer injections, another individual (e.g. partner, caregiver, relative or a healthcare professional) may perform home-administration who has accompanied the participant to the site and has been trained on and demonstrated ability to correctly administer the subcutaneous injections. The participant may also continue to have injections at the site if this is the participant's preference.

If a participant is unable to travel to the investigative site for their study visit, shipment of study treatment from the site to the participant's home may be available in cases of a pandemic or a national and/or global emergency.

Doses on Week 1 (dose #2) and Week 2 (dose #3) should be administered no more than +/- 1 day. If the dose on Week 1 (dose #2) is missed, the dose due on Week 2 (dose #3) should be adjusted to 7 days after dose #2 was given.

If a monthly injection of ofatumumab is missed, it should be administered as soon as possible without waiting until the next scheduled dose. Subsequent doses should be administered at the recommended intervals (+/- 3 days).

Participants will be instructed to contact the investigator/site staff prior to self-administration at home if they are experiencing any AE/SAEs or have any concerns. Participants will record the dates of all at-home study treatment doses.

Participants will be provided with the following items to facilitate the at-home injections of study treatment: an insulated bag with cool gel packs to transport the study treatment from the site to the participant's home; alcohol swabs and gauze pads; a sharps container for immediate disposal of the used syringes; monthly home urine pregnancy test; ofatumumab dose administration and pregnancy test diaries; and a copy of the AI instruction leaflet will be provided which includes detailed information, precautions and instructions for administering subcutaneous injections using the AI pen. This information should be reviewed with the participant (and his/her partner/relative as applicable) to ensure that they understand the correct procedure for self/home administration.

All kits of study medication assigned by the IRT will be databased in the IRT system.

Table 6-4 Arm 1 treatment schedule

Ofatumumab 20mg	BL	D 7	D 14	M 1	M 2	M 3	M 4	M 5	M 6	M 7	M 8	M 9	M 10	M 11	M 12	M 13	M 14	M 15	M 16	M 17
--------------------	----	--------	---------	--------	--------	--------	--------	--------	--------	--------	--------	--------	---------	---------	---------	---------	---------	---------	---------	---------

Key

BL =
Baseline

D = Day

M = Month

Table 6-5 Extension treatment schedule

Ofatumumab 20mg	M 18	M 19	M 20	M 21	M 22	M 23	M 24	M 25	M 26	M 27	M 28	M 29	M 30
--------------------	---------	---------	---------	---------	---------	---------	---------	---------	---------	---------	---------	---------	---------

Key

M = Month

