2.2 Secondary estimands

Not applicable.

3 Study design

This study is an open-label, multi-center, prospective eighteen-month study in a minimum of

118 MS patients with early RRMS (defined as within 6 months of diagnosis of clinically

definite RRMS) and who are disease modifying therapy (DMT) treatment naïve. RRMS patients will be benchmarked against age- and sex-matched healthy controls (n=50) for select secondary [REDACTED]. A screening period of 4 weeks will be used to assess eligibility and the assessment to address the primary objective will be performed at the end of the maintenance period (Month 18). There will be one interim analysis after the last participant completes his/her Month 18 (primary analysis time point) visit. Participants who complete the treatment period or who prematurely discontinue study drug and the study, and do not continue on any MS DMT, will undergo a safety evaluation 100 days following last dose of study treatment (captured only in source documents and only for ofatumumab treated participants), and will be discharged from the study if they choose to not be included in the optional extension portion of the trial for an additional 12 months (up to 30 months total in trial). Healthy control participants will not have a safety evaluation post end of study. Additional efficacy and safety assessments will be evaluated during the optional open-label extension to further elucidate the long-term clinical and radiological effects of ofatumumab (Figure 3-1). Of note, MRI data will be re-baselined at month 6 to account for treatment-related pseudo atrophy.

[figure not shown]
Eligible participants with RRMS will receive ofatumumab 20mg subcutaneous doses at Baseline/Week 0 (Day 1), followed by Week 1 (Day 7), Week 2 (Day 14) and then every month thereafter, beginning at Week 4 (Month 1) until Month 18 (see Figure 3-1). Additional efficacy and safety assessments will be evaluated up to 30 months, necessitating ofatumumab monotherapy over the course of up to 30 months. Ofatumumab will be administered according to the United States Prescribing Information (USPI). RRMS patients must remain on ofatumumab monotherapy to remain in the trial, with no DMT switching or combination DMT therapy allowed. Healthy controls will not be given a therapy.

Assessments will be performed per the assessment schedule found in Table 8-1.

Figure 3-1 Study design

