There are 3 periods to this trial: Screening (up to 4 weeks), open-label active treatment (from Baseline to month 18), and optional 12-month open-label extension (from month 18 to 30).

For participants who discontinue study treatment and study participation prematurely for any reason before the end of the treatment phase, an End of Study visit must be performed within 7 days of study discontinuation.

Upon completing the trial, study patients can continue ofatumumab therapy on commercial drug.

Safety follow-up:

The Safety follow-up (FU) period will be applicable for the following participants:

- participants who complete the Treatment period on the study drug and do not continue on any MS DMT.
- participants who prematurely discontinue study drug and study participation, and do not continue on any MS DMT.

All Safety FU visits must be scheduled relative to the End of Study (EOS) Visit.

Any RRMS patient starting another MS DMT post-trial discontinuation will not have a FU visit performed.

All patients who elect to not be included in the 12-month extension will be followed for an additional 100 days following the EOS timing for that individual patient. A shorter follow-up time is acceptable if patients select a different approved MS DMT (injectable, infusion or oral) treatment during this period. Patients who do not have access to commercial drug within one day of the EOS Visit must continue into the safety FU phase until they are able to access commercial drug or decline DMT therapy moving forward (up to 100 days maximum).

Safety assessments will include standard clinical laboratory evaluations (hematology), [REDACTED], adverse event, and serious adverse event monitoring. Participants that elect to not continue on a DMT after study and have low levels of quantitative

[REDACTED]

serum immunoglobulins during treatment, especially in patients with opportunistic or recurrent infections, should have immunoglobulins monitored by the trial site until B-cell repletion occurs.

4 Rationale

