¹⁶ Administration of ofatumumab (at study site or at home) should occur after the study visit assessments are performed, if on the same day of the study visit

¹⁷ Study drug self-injection (at-home or on-site) will be performed **monthly**, beginning at Week 4, by all ofatumumab participants

¹⁸ MRI assessment must be completed within +/-7 days of the visit

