10.1.3 SAE reporting

To ensure participant safety, every SAE, regardless of causality, occurring after the participant has provided informed consent and until 100 days following the last dose of study treatment for study completers or until End of Safety Follow-up for premature withdrawals must be reported to Novartis safety immediately, without undue delay, under no circumstances later than within 24 hours of learning of its occurrence. Detailed instructions regarding the submission process and requirements are to be found in the investigator folder provided to each site.

All follow-up information for the SAE including information on complications, progression of the initial SAE and recurrent episodes must be reported as follow-up to the original episode within 24 hours of the investigator receiving the follow-up information. An SAE occurring at a different time interval or otherwise considered completely unrelated to a previously reported one must be reported separately as a new event.

Information about all SAEs is collected and recorded on the Serious Adverse Event Report Form; all applicable sections of the form must be completed in order to provide a clinically thorough report. The Investigator must assess the relationship of each SAE to study treatment, complete the SAE Report Form in English, and submit the completed form within 24 hours to Novartis. Detailed instructions regarding the submission process and requirements for signature are to be found in the Investigator folder provided to each site.

If the SAE is not previously documented in the Investigator's Brochure or Kesimpta® USPI (new occurrence) and is thought to be related to the study treatment, a Chief Medical Office & Patient Safety (CMO & PS) Department associate may urgently require further information from the Investigator for health authority reporting. Novartis may need to issue an Investigator Notification (IN) to inform all investigators involved in any study with the same study treatment that this SAE has been reported.

Suspected Unexpected Serious Adverse Reactions (SUSARs) will be collected and reported to the competent authorities and relevant ethics committees in accordance with EU Guidance 2011/C 172/01 or as per national regulatory requirements in participating countries.

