## 2.4 Treatments (study treatment, rescue medication, concomitant therapies, compliance)

### 2.4.1 Study treatment / compliance

The duration of ofatumumab exposure in days for the open-label treatment phase, open-label extension period and overall will be summarized descriptively as a continuous variable using the SAF. The duration of ofatumumab exposure will be calculated within each phase/period and overall, as follows:

- (date of last dose of ofatumumab – date of first dose of ofatumumab) + 1

The date of the last dose of ofatumumab during the open-label treatment phase and the date of the first dose of ofatumumab during the open-label extension period will be determined as outlined in [Section 5.6](#).

Adherence to and persistence on ofatumumab therapy will be evaluated through drug accountability and/or possession diary as outlined in [Section 2.12](#).

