#### 5.6 Ofatumumab dose dates during open-label treatment phase and open-label extension period

The date of the last dose of ofatumumab during the open-label treatment phase and the date of the first dose of ofatumumab during the open-label extension period will be determined according to the following three participant scenarios.

1. Completed Month 18 visit and continued into open-label extension period
  - a. Last dose date of ofatumumab during open-label treatment phase is last dose date < Month 18 visit date
  - b. First dose date of ofatumumab during open-label extension period is first dose date  $\geq$  Month 18 visit date
2. Completed Month 18 visit and did not continue into open-label extension period
  - a. Last dose date of ofatumumab during open-label treatment phase is last dose date  $\leq$  Month 18 visit date
3. Did not complete Month 18 visit
  - a. Last dose date of ofatumumab during open-label treatment phase is last dose date  $\leq$  Month 18 interim analysis data cut-off date
  - b. First dose date of ofatumumab during open-label extension period is first dose date > Month 18 interim analysis data cut-off date

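### For participants not entering the extension, the documents conflict on whether a Month 18 dose is given; separately, the 100-day safety follow-up and the SAE reporting window run from different dates

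*Protocol*

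**What the plan says.** **Dosing at Month 18**

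- Protocol section 6.3.2, "Table 6-4 Arm 1 treatment schedule": baseline, Day 7, Day 14, then M1 to M17. Table 6-5, the extension schedule, runs from M18 to M30.
- Protocol section 6.3.2, text: after the loading doses, "and every month thereafter, beginning at Week 4 (Month 1) until Month 18". The estimand (section 2.1) and sections 3, 4.2 and 6.1.3 describe the regimen in the same way.
- Protocol Table 8-1: the dispensing row and the self-injection row are both marked at M18 for ofatumumab participants. Footnote 17 says that injection is monthly, "beginning at Week 4, by all ofatumumab participants". An extension-only footnote exists (13), but it is attached to the M18 consent cell and not to dispensing or injection.
- SAP section 5.6: for those who continue into the extension, "Last dose date of ofatumumab during open-label treatment phase is last dose date < Month 18 visit date". For those who completed Month 18 and do not continue, the last main-phase dose may fall on or before the Month 18 visit date.

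**Safety follow-up and reporting**

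- Protocol section 3, opening paragraph: eligible participants "will undergo a safety evaluation 100 days following last dose of study treatment".
- Protocol section 3, safety follow-up: "All Safety FU visits must be scheduled relative to the End of Study (EOS) Visit", with 100 days of follow-up after EOS for those who decline the extension. Section 9.3 places their EOS visit at Month 18.
- Protocol section 10.1.1: AE monitoring lasts at least 100 days after the last dose.
- Protocol section 10.1.3: SAEs are reportable "until 100 days following the last dose of study treatment for study completers". For premature withdrawals the window ends with safety follow-up instead.

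**The concern.** A site with a participant leaving at Month 18 can read Table 8-1 as calling for a dose at that visit and Table 6-4 as scheduling none. Sites that resolve this differently will give different numbers of doses under one protocol. The last-dose date, which starts every safety clock counted from last dose, will differ with it.

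The two 100-day anchors are a second, separate inconsistency. For a completer on the nominal schedule they coincide only when the last dose falls on the EOS date. If the last dose is a month earlier, the SAE window closes while the participant is still in follow-up. Table 8-1 footnote 12 keeps follow-up visit data in source documents only, so mandatory SAE reporting is the stated route by which a late event reaches the sponsor.

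**Working it through.** **Inputs.** Doses are counted from Tables 6-4 and 6-5. Target days come from the header of Table 8-1. EOS for participants not entering the extension is Month 18 (section 9.3). The exposure formula in SAP section 2.4.1 is last dose date minus first dose date, plus 1.

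**The plan's own figure.** Table 8-1 puts M3 at Day 90, M6 at 180, M12 at 360 and M30 at 900, which is 30 days per month. Month 18 is then 18 × 30 = Day 540, as stated.

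**Day of M17.** The documents give none. On the same spacing it is 17 × 30 = Day 510; this is an assumption. Table 8-1 places Week 4 (Month 1) at Day 28. Counting from there gives 28 + 16 × 30 = Day 508, or 28 + 16 × 30.4375 = Day 515. The gap to Day 540 is therefore 30 days, with a range of 25 (540 − 515) to 32 (540 − 508).

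**Two readings for a participant who leaves at Month 18**

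| | Last dose M17 | Last dose M18 |
|---|---|---|
| Doses | 3 + 17 = 20 | 20 + 1 = 21 |
| Last dose day | 510 | 540 |
| Exposure, days | 510 − 1 + 1 = 510 | 540 − 1 + 1 = 540 |
| Last dose + 100 | Day 610 | Day 640 |
| EOS + 100 | Day 640 | Day 640 |
| Follow-up beyond the last-dose window | 30 days (25 to 32) | 0 |

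The EOS-anchored date does not move between readings. Only the last-dose-anchored evaluation, AE monitoring and completers' SAE window do.

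**Exposure by period for a continuer.** Under SAP section 5.6 the Month 18-visit dose opens the extension. Main phase: 510 days. Extension: 900 − 540 + 1 = 361 days. The sum is 871, against 900 − 1 + 1 = 900 overall, so 29 days lie between the two periods.

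**Sample size.** 100 / (1 − 0.15) = 117.6, rounded up to 118. The half-widths are 1.96 × √(0.80 × 0.20 / 100) = 7.8% and 1.96 × √(0.85 × 0.15 / 100) = 7.0%. All match the plan and none depends on this point.

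**The case against.** Table 8-1 is a single pooled schedule. M21 to M30 carry no extension label either, so its M18 marks can be read as the first extension dose. Tables 6-4 and 6-5 then join without overlap, and the SAP's rule for continuers fits that split. Footnote 17, taken literally, would dose everyone monthly to M30, so it says little about leavers. The dosing text also points to Figure 3-1, which could not be seen in the text reviewed. All of this stands, and it rules out saying that sites are flatly told both to dose and not to dose. It does not remove the ambiguity: nothing in the tables or text reviewed excludes leavers from the M18 marks, and the SAP makes room for a main-phase dose on that date that Table 6-4 does not schedule.

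A reader might infer that any SAE discovered at the late follow-up visit escapes reporting. Section 10.1.3 goes by when the event occurred, so an SAE that began before the window closed stays reportable whenever it is found. Premature withdrawals are covered to the end of safety follow-up, and the AE monitoring period in section 10.1.1 is a minimum. The gap is confined to late-onset SAEs in one subgroup.

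A reader might also infer that the SAP exposure derivations are wrong. They are workable. A leaver has no extension to which a Month 18 dose could be assigned, the rules use recorded dose dates, and SAP section 2.4.1 nowhere claims that period durations add up to the overall figure. Open-label treatment phase duration is reported separately, and AEs are assigned to phases by the data cut-off, not by last dose. Changing these rules would be a matter of preference.

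Finally, reconciling the Month 18 dose would not settle the anchors. Participants who stop early have an EOS visit tied to study discontinuation, whatever the date of their last dose.

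**Conclusion.** Two limited inconsistencies hold.

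1. For participants who do not enter the extension, the documents do not agree on whether a Month 18 dose is part of the plan. The difference is one dose and about 30 days in the last-dose date. The 30 days rest on the assumed day for M17.
2. The safety evaluation, AE monitoring and completers' SAE reporting count from the last dose, whereas follow-up visits count from EOS. If M17 is the last dose, SAEs with onset in roughly Days 611 to 640 fall within follow-up but outside the stated mandatory reporting window. This applies to completers who decline the extension and take no MS DMT, on nominal visit days. If the last dose is at Month 18, the gap closes for them.

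The documents do not support extending this to efficacy. Section 6.3.2 places any same-day injection after the visit assessments, so a dose at the Month 18 visit cannot affect that visit's NEDA-3 assessments. For extension participants the tables agree that an M18 dose is given.

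**What to change.** - Reconcile Tables 6-4, 6-5 and 8-1 and the regimen text on whether a participant not entering the extension is dosed at the Month 18 visit. The sponsor decides; this review takes no view on which passage is right.
- Use one anchor, or the later of the two dates, for the 100-day follow-up and the AE/SAE reporting window in sections 3, 10.1.1 and 10.1.3, so that reporting always covers follow-up.
- Leave SAP section 5.6 and the exposure formula as they are. At most, footnote the exposure table: the Month 18-visit dose counts as extension for continuers and as main phase for leavers, and period durations do not sum to the overall figure.

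The cost is wording in the protocol tables and follow-up text through an amendment, plus an optional table footnote. The reporting change could add up to about 30 days of SAE reporting for the affected completers. No analysis or sample size changes. For participants who have already left at Month 18, recorded dose dates will show which reading sites followed.
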